3. PATIENT SELECTION

3.1 Eligibility Criteria

3.1.1 Age 18 and older.

3.1.2 Subjects with evidence of AML or MDS that meet at least one of the following criteria:

- Relapsed AML: evidence of $\geq 5\%$ blasts in the bone marrow; or reappearance of blasts in the peripheral blood; or development of

extramedullary disease (according to 2003 IWG criteria [6]) who relapse after:

- Allogeneic hematopoietic stem cell transplant, or
- After one cycle of standard cytotoxic chemotherapy or two cycles of any hypomethylating agent-based therapy
- Refractory AML: ≤ 2 prior induction regimens (example: patients who receive 7+3 followed by 5+2 would count as one induction regimen) or a minimum of two cycles of any hypomethylating agent-based therapy.
- Treatment-naive AML: must be 75 years and older with *de novo* or *secondary* AML to be considered eligible
- Relapsed MDS: disease recurrence after CR, PR or hematologic improvement with bone marrow blasts $\geq 5\%$ who relapse after:
 - Allogeneic hematopoietic stem cell transplant, or
 - After four cycles of any hypomethylating agent-based therapy
- Refractory MDS: disease progression at any time after initiation of hypomethylating agent treatment or persistent bone marrow blasts $\geq 5\%$ despite a minimum of four cycles of hypomethylating agent therapy.
- Untreated or previously treated therapy- related or secondary MDS

- 3.1.3 Allowed prior allogeneic hematopoietic stem cell transplantation (allo-HCT) regardless of stem cell source. Patients must be at least 3 months post allo-HCT (at time of treatment start). Mismatched transplantations would be allowed.
- 3.1.4 Patients must be off systemic immunosuppressive medications >2 weeks prior to treatment start. If patients are on systemic corticosteroids and must be on a dose of prednisone 5 mg/day or less (or equivalent), then patients must be on this reduced dose for >1 week prior to treatment start. Topical steroids are allowed
- 3.1.5 If post allo-HCT, then patient must have baseline donor T cell chimerism of $\geq 20\%$ (from peripheral blood). Evaluation can be made within 4 weeks of treatment start.
- 3.1.6 No limitations on prior therapies.
- 3.1.7 ECOG performance status ≤ 2 (see [Appendix A](#))
- 3.1.8 Participants must have normal organ as defined below:
 - Total bilirubin $\leq 1.5 \times$ local institutional upper limit of normal (ULN)

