- There will be three phases: priming, induction and maintenance
- Hydroxyurea may be used to control leukocytosis
- **Lead In: Priming phase with decitabine alone**
 - **Treatment:** Decitabine 20 mg/m² IV daily over 60 minutes (+/- 15 minutes) x 5 consecutive doses on **days 1-5** given per institutional guidelines
 - **Pre-medication prior to chemotherapy:** per institutional standards
 - Supportive medication such as allopurinol or equivalent should be considered in patients with white blood cell counts $> 10 \times 10^9 / L$ to reduce risk of tumor lysis syndrome.
 - Clinic visits on day 1 and day 15 (+/- 3 days)
 - Labs on day 1 and day 15 (+/- 3 days)
 - Research blood and aspirate collection at the end of the lead in period on a day between days 24-28 (see correlative calendar in [section 10.2](#)).
 - Adverse event evaluation:
 - **Intolerability during priming phase:** If a patient experiences unexpected intolerance to decitabine during the lead in that cannot be ameliorated by supportive care measures, then that patient will not continue on trial and will be replaced.
 - **Graft versus host disease (GVHD):** If there is evidence of acute GVHD that requires the use of systemic corticosteroids agents during the lead in, then the patient will be taken off study due to concern for safety with checkpoint blockade and replaced.
- **Cycles 1-4: Induction phase with combination decitabine and ipilimumab**
 - **Pre-Treatment Requirements**
 - Hematologic criteria to start cycle 1: None required
 - Hematologic criteria to start cycle 2:
 - If there is persistent disease (e.g. peripheral blasts, any marrow disease, persistent leukemia cutis or other form of extramedullary disease) at the time of disease response evaluation at the end of cycle 1, then there are no hematologic requirements to start cycle.
 - In the absence of disease, patients must have an absolute neutrophil count $\geq 500 \times 10^9 / L$ or platelet count to $\geq 25,000 \times 10^9 / L$ to proceed; otherwise administration of treatment will be delayed.
 - Hematologic criteria to start cycle 3:
 - If there is persistent disease (e.g. peripheral blasts, any marrow disease, persistent leukemia cutis or other form of extramedullary disease) at the time of disease response evaluation at the end of cycle 2, then there are no hematologic requirements to start cycle.

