13.5 Analysis of Secondary Endpoints

Safety analyses will be based on the safety population, defined as all enrolled patients receiving at least 1 dose of ipilimumab. Categorical data will be presented as frequencies and percentages. All tests of treatment effects will be conducted at a 2-sided alpha level of 0.05, unless otherwise stated. All tests of interactions will be conducted at a 2-sided alpha level of 0.1, and all CIs will be given at a 2-sided 95% level, unless otherwise stated. Patients who are registered to the study and have received at least one dose of ipilimumab on study will be evaluable for response.

Clinical response to treatment will be assessed following the 2003 IWG criteria for AML [6] and the 2006 IWG criteria for MDS [7]. Anti-leukemic activity will be described in terms of best overall response rate (for AML, to include CR+CRi; for MDS, to include CR+marrow CR+PR+HI), PFS, OS, and remission duration. Time to event summaries will use the Kaplan-Meier method. We will separately evaluate the incidence of acute GVHD and chronic GVHD in patients in the post-allo-HCT cohort, and compare these events with response to treatment.

The focus of this trial is to establish the safety and RP2D of the combination; thus the biomarker studies should be considered exploratory. We will evaluate whether or not absolute lymphocyte count can predict for response for patients who receive combination treatment. ALC levels will be divided into: low (<1000 cells/ul) and normal/high (greater than or equal to 1000 cells/ul). We will compare the response and overall survival of patients with low ALC versus normal/high ALC using Kaplan-Meier estimates and differences will be assessed using log-rank test. We will further capture the absolute change in ALC level measured at baseline to end of cycle 2 (collected prior to dosing on cycle 3 day 1) for response and survival differences. For correlative laboratory tests, we will compare nonrandom measurements in an individual patient either across time (pre-treatment versus on-treatment) with a paired Student *t* test. OS will be censored at the date of last contacts.

REFERENCES

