APPENDIX D ACUTE MYELOID LEUKEMIA RESPONSE CRITERIA

Cheson, B et al., J Clin Oncol, 2003, 4642-9.

Morphological Complete Remission (CR):

-Normalization of the peripheral blood absolute neutrophil count $> 1.0 \times 10^9/L$, platelets $>$ than $100 \times 10^9/L$ no residual evidence of extramedullary disease and bone marrow aspirate with $\leq 5\%$ blasts, no blasts with Auer rods

Morphological Complete Remission with incomplete blood count recovery (CRi):

-Same as CR but without normalization of the peripheral blood absolute neutrophil and platelet count

Relapse from CR or CRi:

-Reappearance of leukemic blasts in the peripheral blood; or $> 5\%$ blasts in the bone marrow not attributable to another cause (e.g. recovery of normal cells following treatment-induced aplasia or use of growth factors) OR
-Appearance or reappearance of extramedullary disease.
-If there are no circulating blasts and no extramedullary disease and the bone marrow blast percentage is $> 5\%$ but $< 20\%$, then a repeat bone marrow performed at least 7 days after the first marrow examination and documenting bone marrow blast percentage $> 5\%$ is necessary to establish relapse.

Partial Remission (PR):

-Normalization of the peripheral blood absolute neutrophil count $1.0 \times 10^9/L$, platelets $>$ than $100 \times 10^9/L$, and at least a 50% decrease in the percentage of marrow aspirate blasts to 5-25%, or marrow blasts $< 5\%$ with Auer rods.

Cytogenetic Responses

Complete cytogenetic response: An abnormal clone is detected in all metaphases prior to treatment and only normal metaphases are observed in all metaphases following treatment.

Partial cytogenetic response: An abnormal clone is detected in all metaphases prior to treatment and the post-treatment sample has 50% or fewer abnormal metaphases compared to the pretreatment value.

Cytogenetic non-response: An abnormal clone is detected in all metaphases prior to treatment and neither complete nor partial cytogenetic response is observed in post-treatment specimens. Specimens with normal cytogenetic results before treatment will not be evaluated for cytogenetic response. The method used to determine cytogenetic response will be standard metaphase cytogenetics.

Stable disease:

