APPENDIX H EUROPEAN LEUKEMIA NET CRITERIA

Table 6. Response criteria in AML

Category	Definition	Comment
Response		
CR without minimal residual disease (CR _{MRD} -)	If studied pretreatment, CR with negativity for a genetic marker by RT-qPCR, or CR with negativity by MFC	Sensitivities vary by marker tested, and by method used; therefore, test used and sensitivity of the assay should be reported; analyses should be done in experienced laboratories (centralized diagnostics)
Complete remission (CR)	Bone marrow blasts <5%; absence of circulating blasts and blasts with Auer rods; absence of extramedullary disease; ANC $\geq 1.0 \times 10^9/L$ [1000/ μ L]; platelet count $\geq 100 \times 10^9/L$ [100 000/ μ L]	MRD [†] or unknown
CR with incomplete hematologic recovery (CR _i)	All CR criteria except for residual neutropenia ($<1.0 \times 10^9/L$ [1000/ μ L]) or thrombocytopenia ($<100 \times 10^9/L$ [100 000/ μ L])	
Morphologic leukemia-free state (MLFS)	Bone marrow blasts <5%; absence of blasts with Auer rods; absence of extramedullary disease; no hematologic recovery required	Marrow should not merely be "aplastic"; at least 200 cells should be enumerated or cellularity should be at least 10%
Partial remission (PR)	All hematologic criteria of CR; decrease of bone marrow blast percentage to 5% to 25%; and decrease of pretreatment bone marrow blast percentage by at least 50%	Especially important in the context of phase 1-2 clinical trials
Treatment failure		
Primary refractory disease	No CR or CR _i after 2 courses of intensive induction treatment; excluding patients with death in aplasia or death due to indeterminate cause	Regimens containing higher doses of cytarabine (see Table 8) are generally considered as the best option for patients not responding to a first cycle of 7+3; the likelihood of responding to such regimens is lower after failure of a first
Death in aplasia	Deaths occurring ≥ 7 d following completion of initial treatment while cytopenic; with an aplastic or hypoplastic bone marrow obtained within 7 d of death, without evidence of persistent leukemia	
Death from indeterminate cause	Deaths occurring before completion of therapy, or <7 d following its completion; or deaths occurring ≥ 7 d following completion of initial therapy with no blasts in the blood, but no bone marrow examination available	
Response criteria for clinical trials only		

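### Appendix D's AML definitions of CR and CRi do not require circulating blasts to be absent, so a patient with leukemia still visible in the blood can be scored a responder

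*Combined protocol and SAP*

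**What the plan says.** Sections 11.1 and 13.5 assign AML response to the 2003 IWG criteria, and 11.1 points to Appendix D for them. The AML response endpoint is CR plus CRi (13.1, 13.5). Section 11.1 gives Appendix H (ELN 2017) a different job, namely deciding progression.

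Appendix D's CR asks for neutrophils above 1.0 x 10^9/L, platelets above 100 x 10^9/L, "no residual evidence of extramedullary disease and bone marrow aspirate with" at most 5% blasts, and no blasts with Auer rods. CRi is "Same as CR but without normalization of the peripheral blood absolute neutrophil and platelet count". Neither entry mentions blasts in the blood.

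Other parts of the protocol treat blood blasts as disease:

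- Section 3.1.2 accepts "reappearance of blasts in the peripheral blood" as one of three alternative ways to qualify as relapsed AML.
- Appendix D's rule for relapse from CR or CRi begins with "Reappearance of leukemic blasts in the peripheral blood".
- Appendix H's CR requires "absence of circulating blasts and blasts with Auer rods; absence of extramedullary disease", and its CRi keeps every CR item except count recovery.
- Appendix E's CR for MDS requires 0% blasts in the peripheral blood.

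**The concern.** A finding that is enough to call a patient relapsed at entry should rule out remission at a later visit. In Appendix D it does not. CRi is the more exposed category: once its two count items are removed, no peripheral blood criterion remains, and the category rests on marrow and extramedullary status alone.

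The CR+CRi rate at the MTD/RP2D is the plan's main description of anti-leukemic activity in AML, and section 1 names preliminary efficacy among the grounds for a later phase 2 trial. The blast omission can only add responders. With 12 to 18 patients per arm at that dose, one added responder visibly changes the rate.

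**Working it through.** **Step 1. Compare the definitions.**

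| Place | Use in the plan | Treatment of blood blasts |
|---|---|---|
| 3.1.2 | Entry as relapsed AML | Sufficient alone |
| Appendix D, CR | AML response | Not mentioned |
| Appendix D, CRi | AML response | Not mentioned; count items also removed |
| Appendix D, relapse from CR/CRi | AML relapse | Sufficient alone |
| Appendix E, CR | MDS response | Must be 0% |
| Appendix H, CR and CRi | Table used for progression only | Must be absent |

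The AML response definition is the only CR definition of the three without a blood-blast item. Appendix H cannot supply it, because 11.1 does not use Appendix H for response. The Auer-rod item excludes only blasts that carry Auer rods. Appendix D's separate line on persistence after transplant uses a threshold above 5% and is not part of CR or CRi.

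**Step 2. Follow one patient through the text.** Take a constructed patient with blasts reappearing in the blood, marrow blasts 3%, no Auer-rod blasts, no extramedullary disease, neutrophils below 1.0 and platelets below 100 x 10^9/L.

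- Entry: meets the relapsed AML definition on the blood finding alone.
- First on-treatment assessment, nothing changed: marrow blasts 3% are within the 5% limit, there are no Auer-rod blasts and no extramedullary disease, and both counts are low. Every written CRi item is met, so the score is CRi.
- With a blood-blast item added: CR and CRi both fail. PR fails because it needs count recovery. Nothing has increased, so progression is not met. Appendix D then gives stable disease.

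**Step 3. Reproduce the plan's precision figures.** Section 13.1 states 90% exact binomial intervals within +/- 25% (6 + 6 = 12 patients) and +/- 21% (6 + 12 = 18). For x responders of n, the Clopper-Pearson limits are the 0.05 quantile of Beta(x, n - x + 1) and the 0.95 quantile of Beta(x + 1, n - x). The widest cases are:

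- n = 12, x = 6: 24.5% to 75.5%, half-width 25.5 points.
- n = 18, x = 9: 29.1% to 70.9%, half-width 20.9 points.

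Both agree with the plan to within rounding or half a point. The concern does not alter them.

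**Step 4. Size of one misclassified patient.** The shift is 1/n.

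- n = 12: 1/12 = 8.3 points. For example, 3/12 = 25.0% (7.2% to 52.7%) becomes 4/12 = 33.3% (12.3% to 60.9%).
- n = 18: 1/18 = 5.6 points. For example, 4/18 = 22.2% (8.0% to 43.9%) becomes 5/18 = 27.8% (11.6% to 49.8%).

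Those denominators combine AML and MDS patients, and the plan gives no split. If, as an assumption, half were AML, the shift in an AML-only rate would be 1/6 = 16.7 points or 1/9 = 11.1 points.

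**Step 5. Total bias.** This would need the proportion of AML patients with few marrow blasts but persisting blood blasts. The documents do not give it, so no total can be computed.

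**The case against.** The best defense is that Appendix D is a short summary headed by a citation, and that the cited 2003 IWG criteria govern. Their full text is not in the documents, so one cannot say whether the source has this gap or only the summary does. Section 3.1.2 attributes its relapse definition to the same source, and the word reappearance in Appendix D's relapse rule presupposes that blasts had cleared. An experienced assessor would probably not call a patient relapsed and in remission on the same finding. This stands as a reason to expect few errors. It does not supply the requirement, because implied clearance is not a listed criterion, and 11.1 directs attention in the blood count chiefly to platelets and neutrophils.

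A reader might also infer more than the text supports:

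- **Response at baseline.** Section 11.1 records best response from the start of treatment and uses the screening marrow as baseline. Screening status is not a response; the problem arises only on treatment.
- **False start of remission duration for CRi.** Section 11.1.1 starts the clocks at CR, PR or (for MDS) HI and does not name CRi. Only a patient meeting both count thresholds, and hence CR, while carrying blood blasts would start a clock wrongly.
- **Three conflicting response labels.** Persistent disease in 5.1 decides whether count criteria apply before the next cycle, and Appendix H decides progression. Neither competes with Appendix D as a response category.
- **A second error in CRi's neutrophil and platelet wording.** Read strictly, a patient with one recovered lineage would be neither CR nor CRi. The category's title, which refers to incomplete count recovery, largely settles this, and a strict reading would remove responders rather than add them.

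**Conclusion.** The omission is real and rests on the protocol's own text: the written AML response rule can score a patient with circulating blasts as CRi and, where counts have recovered, as CR. The effect is upward only, and one patient is worth 8.3 points (n = 12) or 5.6 points (n = 18) with all patients in the denominator, more in an AML-only rate. This assumes Appendix D is applied as written; frequency and total bias are unknown.

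The reach is limited. CR+CRi is a secondary, descriptive endpoint, and section 1 sets no response threshold for moving to phase 2. A reader might infer that the dose decision is compromised, but the DLT definition in 5.2 does not use CR or CRi, so the MTD/RP2D is unaffected.

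**What to change.** In Appendix D, add to CR the requirement that there be *no leukemic blasts in the peripheral blood*. CRi then inherits it, and both agree with Appendix H on this item. Derive it from the CBC with differential that section 5.1 and the 10.1 calendar already schedule with the response marrows at the end of cycles 1, 2, 4, 7 and 10 and at end of study. Optionally, state that CRi means neutrophils and/or platelets not recovered.

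The cost is one phrase, or two with the optional clarification. No visit, sample, sample size or stated interval width changes. The team should confirm that the blast percentage from the differential is captured in the response data. The downside is that the reported response rate may be slightly lower.

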APPENDIX E MDS RESPONSE CRITERIA

Table below from IWG 2006 criteria (Cheson B, Blood, 2006, 419-425)

Category	Response criteria (responses must last at least 4 wk)
Complete remission	Bone marrow: $\leq 5\%$ myeloblasts with normal maturation of all cell lines* Persistent dysplasia will be noted*† Peripheral blood‡ Hgb ≥ 11 g/dL Platelets $\geq 100 \times 10^9/L$ Neutrophils $\geq 1.0 \times 10^9/L$ † Blasts 0%
Partial remission	All CR criteria if abnormal before treatment except: Bone marrow blasts decreased by $\geq 50\%$ over pretreatment but still $> 5\%$ Cellularity and morphology not relevant
Marrow CR†	Bone marrow: $\leq 5\%$ myeloblasts and decrease by $\geq 50\%$ over pretreatment† Peripheral blood: if HI responses, they will be noted in addition to marrow CR†
Stable disease	Failure to achieve at least PR, but no evidence of progression for > 8 wks
Failure	Death during treatment or disease progression characterized by worsening of cytopenias, increase in percentage of bone marrow blasts, or progression to a more advanced MDS FAB subtype than pretreatment
Relapse after CR or PR	At least 1 of the following: Return to pretreatment bone marrow blast percentage Decrement of $\geq 50\%$ from maximum remission/response levels in granulocytes or platelets Reduction in Hgb concentration by ≥ 1.5 g/dL or transfusion dependence
Cytogenetic response	Complete Disappearance of the chromosomal abnormality without appearance of new ones Partial At least 50% reduction of the chromosomal abnormality
Disease progression	For patients with: Less than 5% blasts: $\geq 50\%$ increase in blasts to $> 5\%$ blasts 5%-10% blasts: $\geq 50\%$ increase to $> 10\%$ blasts 10%-20% blasts: $\geq 50\%$ increase to $> 20\%$ blasts 20%-30% blasts: $\geq 50\%$ increase to $> 30\%$ blasts Any of the following: At least 50% decrement from maximum remission/response in granulocytes or platelets Reduction in Hgb by ≥ 2 g/dL Transfusion dependence

APPENDIX F ADVERSE EVENT GUIDANCE AND PRE TREATMENT CRITERIA CHECKLIST

(Note: this is not all inclusive for all visits, but for general study visit only)

- Clinic Visit
- Physical exam
- ECOG score
- Medication review
- Adverse event evaluation and grading if appropriate
- Immune-related adverse event evaluation:
 - Immediately alert Overall PI (required) if there is concern for cardiac toxicity at any time during treatment including clinical signs or concerns for heart failure, myocardial infarction, cardiomyopathy, or myositis. If there is concern for this, obtain at minimum CPK and troponin, cardiology consult, and EKG and echocardiogram, if it is clinically relevant. Please refer to section 6.4.7 for guidance on cardiac toxicity management for ipilimumab.
 - Prior to initiating treatment, always assess stool frequency (bowel movements per 24 hours).
 - Change in bowel habits (colitis)?
 - Blood in the stool, abdominal pain (colitis)?
 - Headache, especially frontal (hypophysitis)?
 - Unusual fatigue, impaired libido (hypophysitis)?
 - Cough, dyspnea (pneumonitis)?
- Labs including minimum of complete blood counts with differential and comprehensive metabolic panel
- Additional immune related labs every 3 months including: gamma GT, direct bilirubin, LDH, TSH and lipase
- If due for ipilimumab: LFTs must be reviewed and must be:
 - $\leq 3.0 \times$ institutional ULN for AST and ALT
 - $\leq 1.5 \times$ institutional ULN for total bilirubin
 - If elevated total bilirubin is due Gilbert's disease or disease-related hemolysis then total bilirubin $\leq 3.0 \times$ institutional ULN
 - If, during the course of treatment abnormal LFT values are detected, ipilimumab should not be administered. The subject should be evaluated and recommendations for management are in section 6 of the protocol with helpful algorithms in [Appendix C](#), as clinically appropriate.

APPENDIX H EUROPEAN LEUKEMIA NET CRITERIA

Table 6. Response criteria in AML

Category	Definition	Comment
Response		
CR without minimal residual disease (CR _{MRD} -)	If studied pretreatment, CR with negativity for a genetic marker by RT-qPCR, or CR with negativity by MFC	Sensitivities vary by marker tested, and by method used; therefore, test used and sensitivity of the assay should be reported; analyses should be done in experienced laboratories (centralized diagnostics)
Complete remission (CR)	Bone marrow blasts <5%; absence of circulating blasts and blasts with Auer rods; absence of extramedullary disease; ANC $\geq 1.0 \times 10^9/L$ [1000/ μ L]; platelet count $\geq 100 \times 10^9/L$ [100 000/ μ L]	MRD [†] or unknown
CR with incomplete hematologic recovery (CR _i)	All CR criteria except for residual neutropenia ($<1.0 \times 10^9/L$ [1000/ μ L]) or thrombocytopenia ($<100 \times 10^9/L$ [100 000/ μ L])	
Morphologic leukemia-free state (MLFS)	Bone marrow blasts <5%; absence of blasts with Auer rods; absence of extramedullary disease; no hematologic recovery required	Marrow should not merely be "aplastic"; at least 200 cells should be enumerated or cellularity should be at least 10%
Partial remission (PR)	All hematologic criteria of CR; decrease of bone marrow blast percentage to 5% to 25%; and decrease of pretreatment bone marrow blast percentage by at least 50%	Especially important in the context of phase 1-2 clinical trials
Treatment failure		
Primary refractory disease	No CR or CR _i after 2 courses of intensive induction treatment; excluding patients with death in aplasia or death due to indeterminate cause	Regimens containing higher doses of cytarabine (see Table 8) are generally considered as the best option for patients not responding to a first cycle of 7+3; the likelihood of responding to such regimens is lower after failure of a first
Death in aplasia	Deaths occurring ≥ 7 d following completion of initial treatment while cytopenic; with an aplastic or hypoplastic bone marrow obtained within 7 d of death, without evidence of persistent leukemia	
Death from indeterminate cause	Deaths occurring before completion of therapy, or <7 d following its completion; or deaths occurring ≥ 7 d following completion of initial therapy with no blasts in the blood, but no bone marrow examination available	
Response criteria for clinical trials only		
Stable disease	Absence of CR _{MRD} -, CR, CR _i , PR, MLFS; and criteria for PD not met	Period of stable disease should last at least 3 mo
Progressive disease (PD) ^{*,†}	
Evidence for an increase in bone marrow blast percentage and/or increase of absolute blast counts in the blood:
 
 >50% increase in marrow blasts over baseline (a minimum 15% point increase is required in cases with <30% blasts at baseline; or persistent marrow blast percentage of >70% over at least 3 mo; without at least a 100% improvement in ANC to an absolute level ($>0.5 \times 10^9/L$ [500/μL], and/or platelet count to $>50 \times 10^9/L$ [50 000/μL] nontransfused); or >50% increase in peripheral blasts (WBC \times % blasts) to $>25 \times 10^9/L$ ($>25 000/\mu$L) (in the absence of differentiation syndrome); or New extramedullary disease 	
Category mainly applies for older patient given low-intensity or single-agent "targeted therapies" in clinical trials
 
In general, at least 2 cycles of a novel agent should be administered
 
Some protocols may require blast increase in 2 consecutive marrow assessments at least 4 wk apart; the date of progression should then be defined as of the first observation date
 
Some protocols may allow transient addition of hydroxyurea to lower blast counts
 
"Progressive disease" is usually accompanied by a decline in ANC and platelets and increased transfusion requirement and decline in performance status or increase in symptoms

Relapse		
Hematologic relapse (after CR _{MRD} -, CR, CR _i)	Bone marrow blasts $\geq 5\%$; or reappearance of blasts in the blood; or development of extramedullary disease	
Molecular relapse (after CR _{MRD} -)	If studied pretreatment, reoccurrence of MRD as assessed by RT-qPCR or by MFC	Test applied, sensitivity of the assay, and cutoff values used must be reported; analyses should be done in experienced laboratories (centralized diagnostics)

ANC, absolute neutrophil count; IDH, isocitrate dehydrogenase; MLFS, morphologic leukemia-free state; WBC, white blood cell.

*The authors acknowledge that this new provisional category is arbitrarily defined; the category aims at harmonizing the various definitions used in different clinical trials.

†Certain targeted therapies, for example, those inhibiting mutant IDH proteins, may cause a differentiation syndrome, that is, a transient increase in the percentage of bone marrow blasts and an absolute increase in blood blasts; in the setting of therapy with such compounds, an increase in blasts may not necessarily indicate PD.

